#### 3) Tertiary Outcomes

- a. *Treatment Engagement*. Is defined here as the # of participants seeing a mental health professional in the month prior to a given assessment (i.e. 3-, 6-, 9-, or 12-month), as indexed by the Treatment History interview.
- b. *Psychiatric Symptoms*. We will utilize the Global Symptom Index from the BSI to assess overall severity of psychiatric symptoms.
- c. *Psychosocial Functioning*. We will compare CLASP vs. SAFE patients on relevant measures of psychosocial functioning, e.g. the WHO-DAS and SS-B.
- d. *Completed suicide*. Given the relatively low incidence of completed suicide, even in this high risk sample, we do not expect to have sufficient numbers of patients who complete suicide for meaningful analyses. However, since completed suicide is a critical outcome, we will track number of completed suicides, using all possible data sources, including significant other reports, chart reviews, community provider reports and reviews of state and national death registries.

**F3.2 Treatment Outcome Analyses.** Effect sizes between patients receiving the CLASP intervention and those receiving SAFE will be computed for each outcome measure. Specifically, for our primary dependent measure (proportion of patients who make suicide attempts), we will calculate an effect size of the difference in the proportions between CLASP and SAFE groups using an odds ratio and its associated robust confidence interval. Effect size estimates will be adjusted by significant covariates in analyses.

Supplanting this estimate will be an analysis of our graded ordinal measure of outcomes. We will employ Generalized Estimating Equations (GEE; [78]) to estimate the ordinal response at each follow-up assessment. GEE have the advantage of providing developed methods for the flexible handling of missing data under various assumptions [79]. Similar analyses will be conducted to obtain estimates for the CLASP effect on the total number of attempts in each treatment condition, suicidal ideation, completed suicide, re-hospitalization due to suicide, and treatment engagement. For continuous indices we will employ robust estimates of effect size obtained in two-level repeated measures analysis [80].

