**C1.1 Subject Characteristics.**

Gender (% female)	68%
Age	43.7 years
Primary Diagnosis	Major Depression – 64%: Bipolar Disorder (depressed) – 24% Mood Disorder NOS – 3.5%: Depressive Disorder NOS – 3.5% Substance Use Disorder – 2.5%: Anxiety Disorder – 2.5%
Lifetime history of suicide attempt	74%
Lifetime history of multiple suicide attempts	47%
Lifetime history of any suicidal behavior (includes preparatory acts, interrupted and/or aborted attempts)	88%
Suicide attempt prior to hospital admission	38%
Any suicidal behavior prior to hospital admission	67%

**C1.2 Acceptability and Satisfaction.** A proportion of patients never engaged in their assigned treatment and were unable to be contacted after discharge from the hospital (24/86 = 28%). Similar proportions of these “non-engagers” were found in CLASP (10/39, 26%) and SAFE (14/47, 30%). Among those patients who did engage in the CLASP intervention, adherence was quite high with approximately 75% of the planned CLASP contacts (in-person and phone calls) completed to both patient and significant other. Satisfaction was also high among patients receiving CLASP, with scores on the Client Satisfaction Questionnaire almost uniformly high (CSQ total score = 29.2). On overall ratings of overall satisfaction, the mean was 3.6 on a scale of 1 (“quite dissatisfied”) to 4 (“very satisfied.”). Similar ratings of satisfaction were also found with the patients who received the SAFE condition (CSQ = 30.5). Although we did not do formal assessment of significant others’ satisfaction, our clinical sense is that significant others were also extremely pleased with their participation. Finally, community providers were quite acceptable to receiving the assessment reports as part of the SAFE procedures – with none of 149 community providers whom we contacted opting out of receiving reports.

**C1.3 Outcomes.** Our two main outcomes were subsequent: a) suicide attempts and b) re-hospitalization due to suicide attempt or risk. We collected six months of data from all possible sources, including follow-up assessments, b) chart reviews, c) significant other reports, and d) community clinician reports. In the table below, we present the conservative intent-to-treatment data, including all patients randomized to each treatment condition, even if they did not participate in the intervention. No patient in the study completed suicide.

# of patients with	CLASP	SAFE	Risk Reduction	95% CI	X 	p	Number Needed to Treat

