## **D2. Participants**

Participants for this study will consist of 200 inpatients from the Providence Veterans Affairs Medical Center and 100 identified significant others. **Inclusion criteria** for the Veteran participant will include: 1) suicide attempt or suicidal ideation with any methods, plan, and/or intent to make a suicide attempt within 1 week of hospitalization as indicated on the hospital chart and/or confirmed by administration of the C-SSRS [48]; 2) age greater than 18 years, 3) have a telephone, and 4) ability to speak, read, and/or understand spoken English sufficiently well to complete the procedures of the study. **Exclusion criteria** will include: 1) diagnosis of primary psychotic disorder based on chart review (e.g. Schizophrenia or Schizoaffective disorder), 2) diagnosis of borderline personality disorder (based on screening with MSI-BPD [49], followed by BPD section of SCID-II if MSI-BPD is positive), or 3) cognitive impairment which would interfere with adequate participation in the project (MMSE [50] < 20).

We will also enroll patients' significant others/family members for those assigned to CLASP intervention; n=100). Significant others will only be recruited to serve as a primary support person for the intervention. Their participation will be limited to 1 joint-family session with the Veteran participant and a series of phone sessions. All sessions will be focused on the Veteran participant. Significant others will not be asked to complete any questionnaires or interviews and no personal information other than name and phone number will be collected. **Inclusion criteria** for significant others will include: 1) age greater than 18 years, 2) have a telephone, & 3) ability to speak, read, and/or understand spoken English sufficiently well to complete the procedures of the study.

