#### **F5. Statistical Power**

Statistical power was based upon effect size estimates derived from the CLASP pilot as well as our judgment about how large a difference would represent a clinically significant difference. In our pilot study, for suicide attempts, we found that 3 of 39 (~8%) individuals assigned to CLASP made a suicide attempt compared to 10 of 47 (~21%) randomized to control, yielding an effect size between small and medium ( $d = .38$ ; 95% CI: .31 - .45). Similarly, for psychiatric re-hospitalization, we found that 8 of 39 (~20.5%) individuals assigned to CLASP were re-hospitalized for suicide risk compared to 17 of 47 (~36%) randomized to control, yielding an effect size between small and medium ( $d = .35$ ; 95% CI: .28 - .41). Consequently, we believed that it was important to power the proposed study for effect sizes slightly larger than small ( $\sim d = .25$ ) to provide adequate coverage for the full range of expected effect sizes.

Sample size for effect size and odds ratio comparisons for the primary treatment outcomes was estimated using Fisher's Exact Test using our primary treatment outcome, # of suicide attempts. Assuming the proportions identified in the CLASP pilot,  $\alpha = .05$ , a one-tailed hypothesis test, and our projected sample of 200, our power estimate for this conservative test will be .82. It should also be noted that given the longer follow-up period in the current study, we hypothesize that the difference in

proportions obtained in our pilot study are likely to be higher due to the longer period of risk assessed. Consequently, the proposed study design should have ample power to test our primary hypothesis.

To estimate power for latent growth curve models, we used Zhang & Wang's [81] simulation procedure for SAS 9.1.3. Our simulation assumed five repeated measures assessments (Baseline, 3-, 6-, 9-, and 12-month), a moderate correlation between slopes and intercepts ( $r = .30$ ), a total missing data rate of ~30%, and 2500 simulation replications per sample size. We simulated sample sizes ranging from 50 to 300 in 10 participant intervals for our lower-bound effect size estimate ( $d = .28$ ). The proposed sample of participants ( $N = 200$ ) should be adequate (Power > .80) to detect even our lower-bound effect size for the full sample.

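### The primary odds ratio for 12-month attempts takes no account of how long each patient was observed, although non-contact was common in the pilot and scheduled contact differs by arm; F5's .82 makes no allowance for loss

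*Combined protocol and SAP*

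**What the plan says.** F3.2 defines the main comparison: "for our primary dependent measure (proportion of patients who make suicide attempts), we will calculate an effect size of the difference in the proportions" between the arms, using an odds ratio with a robust confidence interval, adjusted for significant covariates. F3.1 sets the window at 12 months and draws attempts from C-SSRS interviews, hospital charts, significant-other reports and clinician reports. Total attempts are also counted, with no mention of observation time.

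F5 gives the power. The sample size "was estimated using Fisher's Exact Test using our primary treatment outcome, # of suicide attempts". With the pilot proportions ("3 of 39 (~8%) individuals assigned to CLASP made a suicide attempt compared to 10 of 47 (~21%) randomized to control"), "a one-tailed hypothesis test, and our projected sample of 200, our power estimate for this conservative test will be .82". Later in F5, the growth-curve simulation assumes "a total missing data rate of ~30" percent.

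Section C1.2 reports that some pilot patients never engaged and "were unable to be contacted after discharge from the hospital (24/86 = 28" percent). Section C1.3 presents pilot outcomes "including all patients randomized to each treatment condition, even if they did not participate in the intervention".

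Missing data are otherwise covered only in general terms. F1 names likelihood methods under missing at random, as appropriate. F3.2 names GEE for an ordinal outcome without choosing a missing-data assumption. No time-to-event analysis is planned.

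**The concern.** A yes/no proportion over 12 months is well defined only if status is known for everyone over 12 months. Where it is not, an odds ratio with no further method must either keep the patient as attempt-free or leave the patient out. Neither uses the length of time observed.

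Unequal observation is plausible here. Both arms have the same research interviews, but D6.1 gives CLASP four in-person meetings and a target of 11 telephone contacts, with parallel calls to the significant other. SAFE has assessments and clinician reports only. If SAFE patients are lost sooner, more of their attempts go unseen and the treatment effect looks smaller than it is. The .82 in F5 would then overstate the chance of detecting it.

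**Working it through.** **Inputs from the documents.** Proportions 3/39 = 7.69% and 10/47 = 21.28%; one-tailed alpha .05; Fisher's exact test; N = 200 (all F5). The allocation ratio is not stated; 100 per arm is inferred from D2 ("those assigned to CLASP intervention; n=100").

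**Assumptions.** The pilot proportions are the true 12-month risks. Of the attempts, 40% fall uniformly in months 0–3 and 60% uniformly in months 0–12, in line with the early risk described in B2. Patients who are lost leave at 0, 3, 6 or 9 months with probabilities .40, .25, .20 and .15. The loss rates themselves are illustrative.

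**Step 1: reproduce .82.** Power is the sum, over all pairs of event counts, of the product of the two binomial probabilities, counting pairs with one-sided Fisher p ≤ .05. At 100 per arm this is .833 with the exact pilot fractions and .799 with 8% and 21%. The stated .82 lies between, and needs outcome status for all 200.

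**Step 2: some patients contribute no outcome, risks unchanged.** With 15% missing (85 per arm) power is .762. With 30% missing (70 per arm) it is .676. With 8% and 21% the figures are .724 and .636.

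**Step 3: lost patients stay in the denominator as attempt-free.** The share of attempts that has occurred by month t is F(0) = 0, F(3) = .40 + .60 × 3/12 = .55, F(6) = .70, F(9) = .85. The chance that a lost patient's attempt was seen before loss is .40×0 + .25×.55 + .20×.70 + .15×.85 = .405. If records find half of the later attempts, it becomes .405 + .5 × .595 = .7025.

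Observed proportion = true risk × [(1 − loss) + loss × chance seen]. For loss of 20% in CLASP and 40% in SAFE, with no record capture:
- CLASP: 7.69% × (.80 + .20 × .405) = 7.69% × .881 = 6.8%
- SAFE: 21.28% × (.60 + .40 × .405) = 21.28% × .762 = 16.2%
- Odds ratio: (.0678/.9322) / (.1621/.8379) = .38, against a true .31

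**Step 4: power, one-tailed, 100 per arm.** Fisher power is exact, from the observed proportions. The other two columns come from a 4,000-replicate simulation of the same model. The log-rank test uses events up to last contact, censors there, and ignores record-only events.

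| Loss CLASP / SAFE | Later attempts found in records | Observed CLASP v SAFE | Odds ratio | Fisher | Uncorrected test of proportions | Log-rank |
|---|---|---|---|---|---|---|
| none | – | 7.7% v 21.3% | .31 | .83 | .88 | .88 |
| 30% / 30% | none | 6.3% v 17.5% | .32 | .74 | .81 | .82 |
| 30% / 30% | half | 7.0% v 19.4% | .31 | .79 | .85 | .82 |
| 20% / 40% | none | 6.8% v 16.2% | .38 | .61 | .69 | .82 |
| 20% / 40% | half | 7.2% v 18.7% | .34 | .74 | .80 | .81 |

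Separate simulation runs of this set-up differ by up to about .03 (for example, .76 and .83 in the last row for Fisher and log-rank).

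With equal loss, the log-rank test does no better than the uncorrected test of proportions, give or take simulation error, so its lead over Fisher is mostly Fisher's conservatism. With unequal loss and no record capture, the gap (.82 against .69) remains after that is set aside.

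**The case against.** Much can be said for the plan, and most of it limits the size of the point.

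- **The 30% is not an attrition figure for attempts.** A reader might infer that F5 expects 30% of primary outcomes to be missing. It does not: the rate is an input for five repeated measures. Attempts also come from charts and clinicians, and D5 allows telephone interviews and follows patients whether or not they stay in treatment. Primary loss could be anywhere from near zero to 30%.
- **A reader might infer that true power is .68.** The pilot fractions already include patients who could not be contacted, so removing a further 30% partly double counts. If all pilot attempts were among engagers (39 − 10 = 29 and 47 − 14 = 33), the rates would be 3/29 and 10/33, and power at 70 per arm would be .88. With 3/29 and 8/33 it would be .63. F5 also expects a larger difference at 12 months than in the six-month pilot.
- **A reader might infer a raised false-positive rate.** That needs more loss in CLASP. With SAFE's risk in both arms and loss of 40% in CLASP and 20% in SAFE, one-sided Fisher error is about .09. Reversed, as the contact schedule would suggest, it is about .01. Pilot non-engagement was similar (26% and 30%), and no document supports either split.
- **The comparison is not raw.** The odds ratio is covariate-adjusted, and GEE and missing-at-random methods are named. Nor does the plan say that lost patients count as attempt-free or are dropped; that is inferred from silence. What stands is that neither adjustment nor the named methods set a rule for the binary primary outcome or use observation time.
- **Time to event is no cure.** Patients lost at discharge add no information to it either, and the simulation makes censoring independent of risk, which is the very thing in doubt.

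**Conclusion.** The point holds in a limited form and should be dealt with before analysis. The primary odds ratio has no rule for incomplete observation, and the .82 makes no allowance for loss. The harm depends on loss differing by arm. Under the assumed 20%/40% split, Fisher power is about .61 if records find nothing and about .74 to .76 if they find half of the later attempts, against about .81 to .83 for the log-rank test in both cases. With equal loss the odds ratio barely moves (.31 to .32) and the gain is small.

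These figures rest on the pilot proportions as 12-month risks, the assumed timing of attempts and losses, and censoring unrelated to risk. They use F5's Fisher test in place of the adjusted odds ratio. They illustrate sensitivity and do not predict this trial's power. A separate asymmetry remains under either analysis: F3.1 uses significant-other reports, but D2 enrolls significant others only for CLASP.

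**What to change.** **F3.1 and data collection.** Record the date of each attempt and the last date on which attempt status was ascertained, by interview or by a chart review applied equally in both arms. A record-only event should count in the main analysis only if the same search also extends observation for patients without an event.

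**F3.2.** Analyse time from randomization to first attempt within 12 months, censored at that last date, with a log-rank test and the difference in Kaplan-Meier 12-month risks. This still answers whether fewer patients attempt. Keep the all-randomized proportion, using all sources, as a sensitivity analysis, and vary the handling of record-only events there. Add a log person-time offset to the model for total attempts.

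**F5.** State that .82 assumes outcome status for all 200. Show power at the pilot proportions over an assumed loss range: about .83 with none, .76 with 15% and .68 with 30% contributing no outcome. Note that the 30% is borrowed from the growth-model input and that the pilot rates may already reflect some loss.

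**Cost.** Plan wording and two date fields; the visit schedule is unchanged, and quarterly interviews, weekly LIFE ratings and charts should supply most dates. The price is the assumption that censoring is unrelated to attempt risk, which is why the proportion stays as a check. The change does not resolve the one-sided availability of significant-other reports.

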## D6. Study Procedures

Research staff will approach potentially eligible participants during inpatient hospitalization in either the medical unit or the psychiatric inpatient unit. If interested, informed consent will be obtained and research staff will coordinate with the Veteran patient and inpatient staff in order to conduct the baseline assessment. Eligible patients will be enrolled in the study.

After enrollment patients will be randomized to 1) Safety Assessment and Follow-up Evaluation (SAFE) or 2) CLASP for a six month period. We will use the urn randomization strategy described by Wei [63] and Stout [64] to help insure balance among treatment groups. Urn randomization is a stratified randomization technique, which randomly assigns patients of a given subgroup to treatment conditions, but systematically biases the randomization in favor of balance among the treatment conditions on the stratification variables. For this study, we will be balancing the treatment groups on the following stratification variables: 1) gender of participant (male or female); 2) number of previous suicide attempts (zero, one, many) and 3) recent intake for suicidal ideation vs suicide attempt. We have successfully used the urn randomization procedure in several previous treatment outcome studies [65, 66] and have acquired an electronic file that contains the algorithm for urn randomization

[67]. This file also will provide the ability to monitor effectiveness of our stratification and randomization procedures. Patients assigned to the CLASP intervention will be asked to identify and reach out to a significant other to participate with them. For those in the CLASP intervention, research staff will attempt to complete 3 in-person individual sessions and 1 in-person joint session while the patient is hospitalized. In the event that the patient is discharged prior to the completion of in-person sessions, those sessions will be scheduled in the 1-2 weeks after the patient has left the hospital and will be conducted in assessment rooms in the Research building.

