## **F2. Baseline differences**

Chi-squares and t-tests will be used to assess the effectiveness of our randomization procedures, (i.e., compare CLASP to SAFE on demographic variables, diagnosis, suicide history and characteristics of previous attempt, and presence and severity of other suicide risk factors).

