#### **F4. Change Trajectory**

We will use latent growth curve modeling to explore the trajectory of change in our outcome measures specified above. These models will initially be specified as parallel growth processes (i.e. simultaneous modeling of suicide attempts, suicidal ideation, and psychiatric hospitalization) to account for shared variance, but will be tested individually if a parallel growth model cannot be fit. Using data collected across our 5 assessments, we will estimate intercept (i.e. mean) and slope (i.e. linear rate of increase/decrease) for each of these latent suicide risk constructs. As we expect participants will show clinical improvements at the end of the CLASP protocol, with some participants deteriorating in the follow-up (with a similar, but more pronounced intensity of response for SAFE participants) we will also investigate quadratic slope (i.e. curvilinear change trajectory). To account for time, we will fix our initial two time points, and allow MPlus to estimate the remaining time parameters. We first fit unconditional models to identify the optimal change trajectory for each outcome.

Once the optimal growth trajectory has been identified, we then fit conditional growth models in which growth parameters (i.e. intercept, slope, quadratic slope) are regressed on selected predictor variables (i.e. treatment assignment, covariates, and/or moderator variables of interest). We chose this analytic approach because it permits us to both take advantage of the repeated suicide assessments and to model variations associated with the implementation and cessation of treatment. We will be able to add additional predictors to the model iteratively, to explore the unique and overlapping predictive utility of each measure. However, we recognize that as with any latent variable modeling approach, we may experience difficulty with model fit. In the event that we are unable to fit a model to the data, we will either modify our model (i.e. exclusion of a risk variable, inclusion of covariance between predictors, change in time parameterization, etc.) or employ a simplified multilevel modeling approach (i.e. HLM) or multiple linear regressions.

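### The covariates for the primary odds ratio are left to significance in the data, and the three variables used to balance randomization are not named; fix the model in advance

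*Combined protocol and SAP*

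**What the plan says.** - **D6 Study Procedures** uses urn randomization and states that "we will be balancing the treatment groups on the following stratification variables". The first variable is gender. The others are "2) number of previous suicide attempts (zero, one, many) and 3) recent intake for suicidal ideation vs suicide attempt".
- **F3.2 Treatment Outcome Analyses** takes the proportion of patients with an attempt as the primary measure and summarizes the difference "using an odds ratio and its associated robust confidence interval". The next sentence is the only covariate rule in that section: "Effect size estimates will be adjusted by significant covariates in analyses".
- **F4 Change Trajectory** lets the growth models include "treatment assignment, covariates, and/or moderator variables of interest", again without naming the covariates.
- **F2 Baseline differences** plans tests between the arms: "Chi-squares and t-tests will be used to assess the effectiveness of our randomization procedures". It does not say that the results choose covariates for any outcome model.
- **F5 Statistical Power** bases the primary power figure on an unadjusted Fisher's exact test with "a one-tailed hypothesis test, and our projected sample of 200, our power estimate for this conservative test will be .82".

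Nothing in section F names the three balancing variables as model terms.

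**The concern.** The urn uses three variables thought important enough to balance. The usual companion is an analysis that conditions on them whatever their p-values. F3.2 instead lets the data choose, without saying whether significance means association with the outcome or imbalance between arms, at what level, or from which candidate list. Several reasonable analysts could follow the sentence faithfully and report different primary odds ratios.

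At stake is mainly pre-specification: a primary estimate defined before outcomes are known and aligned with the randomization. A small amount of power is also involved, as is some room to choose among models after seeing the results.

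**Working it through.** **1. The plan's own figure.** Inputs from F5: 3/39 = 7.7% (CLASP), 10/47 = 21.3% (SAFE), one-tailed alpha .05, N = 200. I take 100 per arm, inferred from the 100 significant others planned for CLASP in D2. Exact power of the one-tailed Fisher's test, summing binomial probabilities over all tables with p ≤ .05, is .833. With the rates rounded to 8% and 21% it is .799. These bracket the stated .82. The figure belongs to an unadjusted 2×2 test, so it does not depend on the covariate rule.

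**2. Room for a fixed model.** Expected events: 100 × 10/47 + 100 × 3/39 = 21.3 + 7.7 = 29.0. Parameters besides the intercept: treatment 1 + gender 1 + previous attempts 2 + intake type 1 = 5. That is 29.0/5 = 5.8 events each. If the 30% missing rate that F5 uses for the growth models applied here, as a bound, it would be 0.7 × 29.0 = 20.3 events, or 4.1 each.

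**3. Fixed model against selection by outcome p-value.** 4,000 simulated trials per row, N = 200, urn-type biased coin within the 12 cells, one-sided .05 Wald test. From the pilot table (C1.1): 26/27/47% with no/one/several previous attempts (100 − 74, 74 − 47, 47) and 38% admitted after an attempt. Assumed, because the documents do not give them: 15% women, and odds ratios for gender, one attempt, several attempts and index attempt of 1 throughout (none), 1.5/1.5/2.5/1.5 (moderate) or 2/2/5/3 (strong). The power rows use the pilot rates; the size rows use 10/47 in both arms.

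| Prognostic strength | | Unadjusted | All three fixed | Keep term if \|z\| > 1.96 | All four terms kept | No term kept |
|---|---|---|---|---|---|---|
| None | power | .869 | .868 | .870 | 0% | 85.4% |
| None | size | .052 | .052 | .053 | 0% | 83.0% |
| Moderate | power | .869 | .874 | .872 | 0.1% | 48.1% |
| Moderate | size | .046 | .051 | .050 | 0.3% | 32.5% |
| Strong | power | .884 | .901 | .900 | 1.4% | 7.1% |
| Strong | size | .043 | .050 | .050 | 4.4% | 1.1% |

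Selection by significance almost never keeps the whole balancing set. It does not inflate size. The power gain from the fixed model runs from about 0 to 1.7 points.

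**4. How far the readings diverge.** A second set of simulations used one urn per factor level, 5 to 20% women and other assumed strengths. It compared four readings: baseline imbalance at .05, and three outcome-based rules.
- At pilot rates their odds ratios differed by a median factor of 1.05 to 1.15.
- The one-tailed verdict differed from the fixed model's in 1.8 to 4.5% of trials.
- Size was .047 to .059 for the readings and .051 to .058 for the fixed model.
- Power was .868 to .895 for the fixed model and .863 to .886 unadjusted, a gain of 0.1 to 2.0 points.
- The robust 95% interval of the fixed model covered in 94.1 to 95.6% of trials, and in 92.9 to 95.7% with 30% loss.

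**5. Which odds ratio.** At pilot rates the marginal odds ratio is (3/36)/(10/37) = .308. The conditional one was .285 to .300 under the assumed strengths, 3 to 8% lower (1 − .300/.308; 1 − .285/.308).

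**6. Sparse levels.** At 10% women and pilot rates, some level of gender or attempt history had no events in 6 to 12% of simulated trials. The treatment term nearly always stays estimable, but the coefficient of the empty level diverges.

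**The case against.** The strongest reply is about weight. Fisher's exact test is the only test the plan ties to the primary outcome. If it decides the trial, the covariate rule touches only the reported effect size. Even otherwise, the power gain is at most about 2 points with complete data, and few verdicts change. This stands, and it limits how strongly the point can be put.

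Three stronger inferences are tempting, and the documents do not support them.
- **F2 is the selection rule.** If it were, it would work against the urn: each balancing variable came out significant in only 1.4 to 3.4% of simulated trials. But F2 gives its purpose as checking the randomization and is never linked to F3.2. It is one possible reading, not a stated rule.
- **The rule inflates type I error.** No mechanical reading did. Deliberately taking the most favourable of five specifications gave .055, and of all eight subsets of the three variables .057, against .045 to .048 for each rule alone (Monte Carlo error .004). That is small, and the plan does not propose such picking.
- **The test must become model-based.** Naming covariates for the estimate does not require this. Fisher's test has exact size .036 at 10/47 and .034 at 13/86 in both arms, so dropping it would give up a conservative test for a separate reason.

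Sparse data is a fair practical objection. A fixed model needs a stated rule for empty levels, or one data-dependent choice replaces another.

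**Conclusion.** The point holds as a question of pre-specification with modest numerical consequences. The plan balances on three variables, then ties the primary odds ratio to an undefined significance rule, so those variables may be omitted and the estimate is not fixed in advance. Expect no inflation from any mechanical reading, about 0 to 2 points of power from adjustment with complete data, and a different verdict in about 2 to 4% of trials if the adjusted odds ratio carries the test. If Fisher's test carries it, only the effect estimate is affected.

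These sizes rest on the pilot rates and pilot case mix, and on assumed prognostic strengths and proportions of women. The pilot's index-attempt share is itself given two ways: 38% in C1.1, and 35/86 = 41% in C1. D6 does not say whether the count of previous attempts includes the index attempt. The absence of the balancing variables from section F depends on none of these assumptions.

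**What to change.** In F3.2, for the primary outcome, state:

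> The primary odds ratio for any suicide attempt over 12 months will be estimated by logistic regression on treatment, gender, previous attempts (zero/one/many) and intake type, coded as in the urn, and reported as a conditional odds ratio with its robust 95% confidence interval. No covariate is added to or dropped from this model on the basis of significance; other adjustments are sensitivity analyses. If any level of a covariate has no events or the fit does not converge, a Firth-penalized fit of the same model will also be reported.

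For the other outcomes, keep a covariate sentence in F3.2, but name the covariates in advance, outcome by outcome, rather than by significance.

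State which analysis carries the primary test. Either keep the one-tailed Fisher's exact test behind the .82, with the adjusted odds ratio as the effect estimate, or use the treatment term of this model and note in F5 that the .82 is for an unadjusted Fisher's test.

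The cost is a few sentences. The variables are already collected for the urn, and N is unchanged. The downsides are about 29 expected events for 5 parameters, some under-coverage of the robust interval if losses are heavy, and a conditional odds ratio slightly different from the marginal one.
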